Return 24h urine ^h				X										X
Study capsules ⁱ				X			X		X		X			X
Study powder packet ^j				X			X		X		X			X
Adherence ^k							X		X		X			X

^a Two-item protein intake questionnaire on telephone prescreening.

^b To recruit participants who are underactive at baseline, we will use the RAPA, a validated 9-item questionnaire at prescreening and recruit those with scores <5. Intrastudy, changes in physical activity could modify the anticipated responses to treatment. Therefore, we will assess leisure, household, and occupational activity in the past 40 days with use of the Physical Activity Scale for the Elderly (PASE) questionnaire with 10 items and a score ranging from 0 to 400 with higher scores reflecting greater levels of activity at Baseline and Final Day 2.⁶⁴

^c A stable deuterium (D₃)-labelled creatine capsule (60 mg) will be administered to participants at the Enrollment and Final Day 1 visits. A second void of fasting morning urine will be collected on the Baseline and Final Day 1 and 2 visits for analysis of creatine to creatinine. In a subset of participants coming in for a Week 1 safety lab, we will also request a second void of fasting morning urine for analysis of creatine to creatinine on the supplements early in the course of the study. This is to measure the creatine component coming from the diet load.

^d Three consecutive 24-hr dietary recalls will be done for 3 days at the beginning of the study (between the Enrollment and Baseline visits). The third recall day will coincide with the 24-hr urine collected. We will also collect 24-hr recalls on weeks 6, 12, 18, and Final Day 2 to track their diet during the study.

^e Our research dietitian will counsel participants on how to mix the powder packets in water at Baseline and provide a variety of flavors. On weeks 6, 12, and 18, the dietitian will be providing counseling to maintain protein intake in self-selected diets intra-study.

^f Screening blood for routine fasting blood chemistries including serum creatinine (Cr), potassium (K), HCO₃⁻.

^g Fasting study blood:

- Baseline: serum 25-hydroxyvitamin D (25OHD), IGF-1, HCO_3^-
- If the participant is on an ARB, ACEI or potassium-sparing diuretic, a 1 week safety blood for serum K will be drawn. A 6 week safety blood draw to check serum K and Cr (for GFR estimation) will be drawn in all participants.
- At Final Day 2: IGF-1, HCO_3^-
- Ten 0.5 ml aliquots of serum will be archived on the Baseline visit and Final 2-wk visit.

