^h Return 24-hr urine

- Baseline visit and Final 2 visits: Ni, NAE, Cr
- Five 5-ml aliquots will be archived at the Baseline and Final 2 visits.

ⁱ Capsules of KHCO_3 /placebo and Ca/D supplements dispensed. Participants will take 1 capsule after each meal for 14 days (to adapt to the KHCO_3) and then increase to 2 after each meal (6/d total) thereafter.

^j Protein packets will be dispensed by the dietary team. Subjects will take the whey protein supplement with each meal except on the days 164 and 168 (Final Days 1 and 2) when they will skip the packet with their evening meal. The goal of the packets is to bring total intake of protein to 1.5 g/kg/d (or 15-25 g of additional protein with each meal depending on body weight).

^k Adherence to study pills will be assessed by capsule counts and by capsule diaries. Adherence to the protein packets will be assessed by packet counts and diaries. Objective measures of adherence are NAE and UNi.

Medical history questionnaire

The medical history includes medication and supplement use, general medical history, and past and current cigarette smoking and alcohol use. The questionnaire will be conducted in person or by telephone if preferred by the study participant.

Study interventions

Whey protein powder. Protein packets will contain 15-25g of whey protein each. We will advance all participants to

Weight category	A (< 70 kg)	B (70 – 90 kg)	C (91+ kg)
Dosing group	15g per meal	20g per meal	25g per meal

approximately 1.5 g/kg/d based on their body weight and typical baseline protein intake. The whey protein and its isocaloric placebo (maltodextrin - an easily digestible flavorless starch) powder will be flavorless and purchased in bulk at <http://www.bulkfoods.com>. The dietary team will make the packets and distribute to participants at baseline and weeks 6, 12, and 18. The packets will be mixed with water and the dietary team also will provide a menu for how to incorporate the powder into recipes. The whey and placebo powder packets will be isocaloric.

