Bloods will be drawn after a 12-hr overnight fast and between 7 and 9:30 am. All samples from individual participants will be batched for analyses. Serum K, HCO_3^- , serum chemistries, Cr and urinary Cr will be measured on an automated clinical chemistry analyzer (Olympus AU400, Olympus America Inc, Melville, NY). Estimated GFR will be assessed from serum Cr with use of the Modification of Diet in Renal Disease (MDRD) Study equation (see *Exclusion Criteria* in the *Protection of Human Subjects*). Serum 25OHD levels will be measured by LC/MS/MS on a Waters Acquity UPLC with TQD triple quadrupole mass spectrometer with a coefficient of variation (CV) of 6%. Separation is on a C18 UPLC column. NIST 25OHD standards are run to calibrate the assay. Serum IGF-1 will be measured by chemiluminescent immunoradiometric assays on an automated immunoassay system (IMMULITE® 1000, Diagnostic Product Corporation, Los Angeles, CA). The CV ranges from 3.0 to 9.0%. Urinary nitrogen will be measured with a model FP-2000 nitrogen/protein determinator (LECO, St. Joseph, MI) with intra- and inter-assay CVs of 6.5% and 8.6%. Urinary NAE (=titratable acid + NH_4^+ - HCO_3^-) will be measured by a modification of the Jorgensen titration method⁷⁶, as described by Chan,⁷⁷ with precision in our laboratory of 10.1%.⁷⁸

ETHICS AND PROTECTION OF HUMAN SUBJECTS

Human Subjects Involvement, Characteristics and Design

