This proposal involves the participation of human volunteers in a 2x2 factorial design, double-blind, randomized, placebo-controlled study. Participants take an added whey protein packet to achieve a 1.5 g/kg/d protein intake or isocaloric placebo daily with meals and either a KHCO_3 81 mmol/d supplement or a matching placebo daily over a 24-wk period to assess changes in lower extremity muscle power, endurance, handgrip, physical performance, lean and muscle mass, and 24-h UNi excretion. Participants agree to attend up to 9 intrastudy visits (Screening, Enrollment, Baseline, week 1 if on certain medications ONLY, week 6, week 12, week 18, Final Day 1 and 2). These visits will involve (1) a blood draw (Baseline, week 1, week 6, and Final Day 2), (2) return of a 24h urine collection (Baseline and Final Day 2), (3) second fasting urine sample (Baseline and Final Day 1 and 2), (4) double leg press power testing, knee extensor strength testing (Baseline week 12, and Final Day 2), (5) diet recall interviews in person (Baseline, week 6, week 12, week 18, and Final Day 2), (6) hand grip, modified SPPB test, and whole body DXA scan for body composition analysis (Baseline and Final Day 2), and (7) physical activity and medical history questionnaires (Baseline and Final Day 2). Up to 300 men and women age 65 years and over will be screened to attain 120 completers. Participants will be generally healthy and will continue their usual diet and activity level. We will include participants on ≤ 0.8 g/kg/d of dietary protein and are underactive. The study will be conducted at the Jean Mayer USDA HNRCA at Tufts University.

Sources of Materials

At the screening visit, records will be made of the response to screening questionnaires, medical history and physical examination, electrocardiogram, and laboratory results. Daily dietary protein at baseline will be confirmed. Daily physical activity will be assessed. During the course of the study, additional data in the form of records from visits, responses to questionnaires, and testing procedures will be obtained.

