- monitor serum potassium (K) at baseline, 6 wks on full 81 mmol/d dose and at the end of study at 24 wks. In addition, we will measure serum K at 1 week if the participant is on an ACEI, ARB or potassium sparing diuretic. We will measure serum K at any other time, should a participant experience an AE which might be related to the trial. In the unlikely event that it is elevated, the measurement will be repeated immediately. If the repeat measure is elevated, all study pills will be stopped. Serum K will be re-measured after one day off of the study pills to ensure that it has returned to normal. If it remains elevated, the participant will be referred immediately to his/her doctor. Discontinuation of study medications will be managed without unblinding. Participants will be encouraged to remain in the study and complete measurements per protocol to be included in the intention to treat analysis. One exception to this is if a participant develops a "serious" AE in which case he/she will not be asked to remain in the study. If there is an AE which is thought by the staff to be "probably related" or "related" to the coded medication, the PI, when necessary for the safety of the participant, will contact [name], the unblinded team member, and ask her to provide the treatment assignment to the participant's physician. A detailed written report will be submitted to the IRB.

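### Serum K and GFR are required at 24 weeks but are missing from the Final Day 2 blood list, and one of the three GFR stop rules leaves out the powder

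*Protocol*

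**What the plan says.** **24-week safety labs.** The list of intra-study safety steps (Protocol, Ethics and Protection of Human Subjects, under Protection of study blinding) says to "monitor serum potassium (K) at baseline, 6 wks on full 81 mmol/d dose and at the end of study at 24 wks". The next item in that list calls for GFR at week 6 and again at the 24-week visit.

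The schedule is narrower. Footnote g to the procedures chart in Study Design provides for week 6: "A 6 week safety blood draw to check serum K and Cr (for GFR estimation) will be drawn in all participants". It also lists a week 1 K for users of an ACE inhibitor, ARB or potassium-sparing diuretic. For the last visit it reads "At Final Day 2: IGF-1, HCO_3", and adds only stored samples: "Ten 0.5 ml aliquots of serum will be archived on the Baseline visit and Final 2-wk visit". Footnote h, on the 24-hour urine, has "Baseline visit and Final 2 visits: Ni, NAE, Cr".

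**GFR stop rules.** The same safety list gives three routes to stopping after a GFR below 45. Two of them (no repeat obtained; repeat also below 45) stop both powder and pills. The third (repeat of 45-50, then below 45 at the follow-up) stops capsules and does not mention powder.

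**The concern.** Visit staff usually order blood from the schedule, and here the schedule omits two tests that the safety text requires. The protocol's adverse event reporting section sends abnormal laboratory results to adverse event forms, and the safety steps make any GFR below 45 an adverse event. SAP 7e then counts participants with adverse events by randomization group. If K and creatinine were not run at 24 weeks, abnormalities that only a blood test would find could not reach that table, and a reader could take an untested group for an event-free one. An abnormal final value would also get no repeat and no referral.

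The GFR rule matters for a different reason. The protocol gives higher protein intake as one of its grounds for monitoring GFR. A rule that stops the capsules and says nothing about the protein leaves open the exposure it was partly written to guard against.

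**Working it through.** No formula in the plan is in dispute, so the check sets the texts side by side.

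**Step 1. Same visit?** 24 weeks x 7 = Day 168, which the chart labels Final Day 2. Both texts describe the same visit.

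**Step 2. Serum K and serum creatinine, by time point.**

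| Time | Safety steps | Footnotes f and g |
|---|---|---|
| Screening / baseline | K | Screening (f): Cr, K and HCO3-. Baseline (g): 25OHD, IGF-1 and HCO3-, no K |
| Week 1, selected drug users | K | K |
| Week 6 (Day 42) | K and GFR | K and Cr |
| Between weeks 6 and 24 | nothing routine | nothing |
| Week 24 (Day 168) | K and GFR | IGF-1 and HCO3-; neither K nor Cr |

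Of the two safety analytes required at week 24, the blood list carries none.

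**Step 3. Does another section fill the gap?**
- Footnote h's creatinine is measured in urine, while the Biochemical measurements section says: "Estimated GFR will be assessed from serum Cr with use of the Modification of Diet in Renal Disease (MDRD) Study equation". Urinary creatinine alone does not meet that definition.
- Biochemical measurements lists serum K and Cr as assays but gives no time points.
- Human Subjects Involvement confirms that blood is taken: "a blood draw (Baseline, week 1, week 6, and Final Day 2". It names no analytes.

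No other section assigns either test to Final Day 2.

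**Step 4. Size.** The plan is for 120 completers, 30 per arm. Tests missed at week 24 number 0 if staff follow the safety steps. If staff follow footnote g, the number is up to 120 x 1 = 120 for each analyte, or up to 30 per arm. The documents do not say which happened.

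**Step 5. Is a dosing decision lost?** On powder supply: "The dietary team will make the packets and distribute to participants at baseline and weeks 6, 12, and 18". The last supply therefore runs to about the final visit. A stop order at Day 168 would have almost nothing left to stop.

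**Step 6. The three GFR rules, each starting from a value below 45.**

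| What follows | Powder | Capsules |
|---|---|---|
| No repeat obtained | stop | stop |
| Repeat below 45 | stop | stop |
| Repeat 45-50 | not mentioned | continue |
| ...then below 45 again | not mentioned | stop |

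The outer limit for the last row assumes a first value at Day 42, a repeat at Day 43 and a follow-up within the next week (Days 44 to 50). Extra days on powder then run from 0, if staff stop it anyway, to between 168 - 50 = 118 and 168 - 44 = 124. Capsules are taken two after each meal, six a day, so there are three meals. The whey dose is 3 x 15 = 45 to 3 x 25 = 75 g/d in the whey arms. The documents give no frequency for this sequence.

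**The case against.** The strongest reply is that the safety steps order the 24-week tests outright and footnote g does not cancel them, so this is an omission from a list. Footnote g is not a full K list in any case: its Baseline line leaves out K although the safety steps require it there, and the screening K may serve. That has force against treating the list as exhaustive. It does not remove the problem, because footnote g does carry the week 1 and week 6 safety labs and drops them only at the end.

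The protocol also mentions a Manual of Operating Procedures, which is not among the documents and may have ordered the tests. A reader might infer that end-of-study safety data were lost; the documents do not show that.

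A reader might also infer that the omission leaves participants unmonitored from Day 42 to Day 168. It does not create that interval. The safety steps themselves schedule no routine K or GFR between weeks 6 and 24, and K can be measured at any time for a related adverse event. The discrepancy concerns one test occasion, at Day 168. Nor is there a case for attaching a confidence bound to late hyperkalemia: SAP 7e plans no statistical testing of harms and mentions no such bound, and week 6 K at full dose is drawn in everyone.

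The prior data are reassuring. In the team's 12-week dose-finding trial, high K was confirmed in 1 of 79 on placebo and 1 of 79 at 81 mmol/d. A 6-month study of 90 mmol/d potassium citrate in 52 women reported one episode, during dose escalation.

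On the third GFR rule, the wording may be loose drafting. It does not order powder to continue, the participant is referred for care, and the sequence should be rare in people enrolled at a GFR of 50 or more. All of that stands and limits the weight of the point.

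**Conclusion.** Both parts hold as internal inconsistencies, of minor to should-fix weight. The 24-week serum K and serum creatinine are required in one place and missing from the list staff are likely to use, with 0 to 120 tests of each at stake. The loss, if there was one, is the repeat, the referral and the adverse event entry at Day 168. No dosing decision and no efficacy analysis is affected. That the two texts differ is certain; any loss of data is conditional on what staff ordered, which the documents do not reveal.

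The third GFR rule is a separate gap. Read literally, a participant with two values below 45 could stay on whey. It would be too strong to say that the protocol keeps such a participant on powder, since it is only silent.

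**What to change.** 1. Add serum K and serum Cr (for eGFR) to footnote g's Final Day 2 line, and state that they are run in real time. Biochemical measurements says each participant's samples are batched, and a batched result would come too late for a repeat or referral. In the same edit, say whether the screening K counts as the baseline K.
2. Make the third GFR rule read *stop study powder and capsules*, and state in the 45-50 step whether powder continues.
3. For completed visits, check whether 24-week K and eGFR were obtained, and report the number tested by randomization group in the SAP 7e harms table. If they were not obtained, say so, and consider creatinine on archived final-visit serum if it is still held and the laboratory accepts stored samples. The protocol provides for discarding samples once analyses are complete, so this check should come first. Stored serum cannot replace a timely repeat or referral.

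For remaining visits the cost is two analytes on blood already drawn, on the analyzer the protocol names for K, HCO3- and Cr, with no extra visit. The GFR rule is a wording change. SAP 4a describes randomization in the past tense, so item 3 may be the part that still matters most; it costs a records check and possibly one assay.

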KHCO_3 supplement. The 81 mmol of KHCO_3 is available in six 13.5 mmol capsules daily; an equal volume of microcrystalline cellulose (placebo) will be placed in 6 identical gelatin capsules. All capsules will be taken with 8-oz of water or the supplement drink immediately after meals. On days 1-14, participants will take 1 capsule after each meal (adaptation period to minimize risk of GI intolerance); thereafter, they will take 2 capsules after each meal (6/d). KHCO_3 capsules and matching placebo capsules will be purchased from Life Enhancement Products, Inc. (Reno, NV). Independent analysis by Eurofins (Madison, WI) will be carried out to verify contents.

Dietary intake assessment

Dietary telephone prescreening questionnaire – Usual protein intake in grams per day will be assessed with a two-item questionnaire developed in the NEPS laboratory to target individuals on no more than 0.8 g/kg/day of dietary protein. Each of the two questions has multiple parts. For example, participant responses to the following question: “How many servings of per day do you have of a) meat, poultry, and fish? b) eggs? c) dairy such as milk, yogurt and cheese?” For part a), think of a serving as being about the size of a deck of cards. For part c), think of a serving as a cup of milk or yogurt or 2 slices of cheese. The second question asks about vegetable and other non-animal protein foods. From servings, the questionnaire calculates g/d of dietary protein which we can then arrive at the g/kg/d with a body weight. This daily intake will be reviewed and confirmed at screening with an in-person dietary assessment.

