- monitor GFR after 6 wks in the study and at the final 24-wk visit. GFR will be monitored because the higher protein intake and progressive renal failure increases risk of hyperkalemia. The study inclusion criteria include a GFR \geq 50 ml/min/1.73m². If GFR falls below 45 ml/min/1.73 m², participants will be asked to return for a repeat measurement the following day. Should the participant be unable or unwilling to return for the repeat study blood, study interventions (powder packets and pills) will be discontinued. Participants who fail to show up for repeat monitoring will be contacted and advised to obtain care as soon as possible. If the repeat measure is normal, the participant continues per protocol. If the repeat GFR is below 45 ml/min/1.73 m², the study powder and pills will be stopped and the participant referred to his/her physician for follow-up care. If the repeat GFR is in the range of 45-50 ml/min/1.73m², the participant will remain on study capsules and be asked to return for a follow-up GFR measurement in the next week. If the GFR is again less than 45 ml/min/1.73, the participant will stop study capsules and be referred to his care giver for follow-up. If it is above 45 ml/min/1.73, the participant will continue taking study pills. Participants discontinuing study capsules will remain in the study for the intent-to-treat analysis. The threshold of 45 ml/min/1.73 m² was chosen to allow for some day to day fluctuation in creatinine and hydration status. Any decline below 45 ml/min/1.73 m² will be recorded as an Adverse Event.
- have all pill supplements taken in split doses after meals with a full (8-oz) glass of water to increase tolerability;
- have all powder packet supplements incorporated in each meal in split doses to increase tolerability;
- phase-in treatment for study pills (taking half dose for the first 14 days) to increase tolerability

- have participants who are unable to tolerate an escalation of the study pills or packets remain in the study and take the maximal number of capsules or powder packets that they are able to tolerate.

Data Safety and Monitoring Board (DSMB)

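### The GFR stopping rule stops powder and pills on two routes but names only capsules on the third; probably a drafting slip, and cheap to fix

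*Protocol*

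**What the plan says.** The rule is one bullet in the Protocol's list of intra-study safety steps (Ethics and Protection of Human Subjects, under Protection of study blinding). GFR is checked at week 6 and at the final 24-week visit. A value below 45 ml/min/1.73 m² calls for a repeat the next day, and three routes to stopping follow.

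- **No repeat obtained:** "study interventions (powder packets and pills) will be discontinued".
- **Repeat below 45:** "the study powder and pills will be stopped and the participant referred to his/her physician for follow-up care".
- **Repeat 45 to 50:** "the participant will remain on study capsules and be asked to return for a follow-up GFR measurement in the next week". Then: "If the GFR is again less than 45 ml/min/1.73, the participant will stop study capsules", with referral. If the recheck is above 45, "the participant will continue taking study pills".

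The bullet then adds: "Participants discontinuing study capsules will remain in the study for the intent-to-treat analysis". Its stated reason for the checks is: "GFR will be monitored because the higher protein intake and progressive renal failure increases risk of hyperkalemia". The SAP contains no GFR stopping rule.

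**The concern.** The second and third routes both end with two readings below 45. They differ only in that the third has a value of 45 to 50 in between. One expressly stops the powder and the other does not mention it, and no reason is given. The bullet itself ties the monitoring to protein intake, so the protein product is the one a reader would expect to see named.

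If staff follow the wording literally, a participant with two of three readings below 45 keeps taking the powder. In the whey arms that is 15 to 25 g of protein per meal, or 45 to 75 g/day at three meals (3 × 15 and 3 × 25). What is at stake is the clarity of a safety rule, not the trial's inference.

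**Working it through.** **1. The branches side by side**, each after a first GFR below 45:

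| Next result | Capsules/pills | Powder |
|---|---|---|
| No repeat obtained | stopped | stopped |
| Repeat below 45 | stopped | stopped |
| Repeat 45–50, recheck pending | continue | not mentioned |
| Repeat 45–50, recheck below 45 | stopped | not mentioned |
| Repeat 45–50, recheck above 45 | continue | not mentioned |

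**2. Does the word capsules cover powder?** In the Protocol's Study interventions section they are separate products. KHCO3 "is available in six 13.5 mmol capsules daily; an equal volume of microcrystalline cellulose (placebo) will be placed in 6 identical gelatin capsules". The powder is whey or maltodextrin in packets, which the dietary team makes and distributes. The last item of the same safety list also names capsules and packets separately. Against that, the retention sentence names only capsules although two routes stop both products, so the bullet does use the word loosely at least once. The text does not settle the question.

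**3. Literal effect of the third route by arm** (planned 30 per arm, Objectives and Endpoints):

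- Arm 1, whey + KHCO3: KHCO3 goes from 6 × 13.5 = 81 to 0 mmol/d; whey is not stopped.
- Arm 2, whey + placebo capsule: cellulose is stopped; whey is not. No active product is removed, but there is also no KHCO3 load.
- Arm 3, maltodextrin + KHCO3: 81 to 0 mmol/d; no protein product.
- Arm 4, both placebo: no active product either way.

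The wording can therefore affect protein exposure only in Arms 1 and 2, (30 + 30)/120 = 50% of the planned sample. That is an allocation share. It is not the proportion who would reach the branch.

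**4. Time affected.** The final-visit check falls at the end of treatment, so only the week-6 check matters. With the test on day 42 and the repeat on day 43, a recheck in the following week falls between day 44 and day 50.

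- Recheck day 50: 168 − 50 = 118 days; 118/168 = 70%.
- Recheck day 44: 168 − 44 = 124 days; 124/168 = 74%.

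The Payment plan section allows up to 10 extra days in the study, which could lengthen this slightly.

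**5. Analysis sets (SAP 5c).** ITT follows assignment, so membership cannot change. For the other sets, assume full adherence before stopping and average compliance over both assigned products, placebo included (the SAP does not define the average). Capsules are 3/day for 14 days and 6/day for the next 154: 14 × 3 + 154 × 6 = 966.

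- Capsules stopped at day 50: (42 + 36 × 6)/966 = 258/966 = 27%. At day 44: (42 + 30 × 6)/966 = 222/966 = 23%.
- Powder stopped at day 50: 50/168 = 30%. At day 44: 44/168 = 26%.
- All exceed the 10% mITT cut, so mITT membership is the same whether or not powder stops.
- If powder continues at 100%, the two-product average is (27 + 100)/2 ≈ 63% (day 50) or (23 + 100)/2 ≈ 61% (day 44). Both are below the 75% per-protocol cut, so the participant is outside that set either way.

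Without full adherence the mITT result can change. At 30% powder adherence, stopping at day 50 gives 0.30 × 50/168 = 9%, under the cut, while continuing at 30% stays above it.

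**The case against.** The best reply is that the bullet is silent about powder and does not order it continued. The retention sentence shows capsules used loosely, and a recheck below 45 is in ordinary terms a repeat below 45, for which both products have already been stopped. Sensible staff could well stop both. This stands as a plausible reading, and it is why a drafting slip is the likely explanation. It does not close the point, because the recheck has its own instruction and that instruction names one product.

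A second reply is that a pills-only stop may be deliberate. The preceding bullet answers confirmed high potassium by stopping all study pills, with no mention of powder, and hyperkalemia is the hazard named here too. But that rule has a different trigger, and the GFR rule expressly stops powder on two of its own routes. A pills-only policy does not explain the third.

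A third reply is that protections remain, and they do. Any GFR below 45 is recorded as an adverse event. Non-serious events go to the IRB within 5 days and to the DSMB at its requested interval. Serum potassium is measured for any event that might be trial-related. The participant is referred. Stopping is managed blind, so a reader might infer that nobody could learn whether a capsule stop had removed anything active. That goes too far: for an event judged probably related or related, the PI can, when safety requires, have the assignment given to the participant's physician.

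Finally, the Manual of Operating Procedures may specify what happens to the powder. It is not among the documents.

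**Conclusion.** The inconsistency is real and lies in an operative safety rule, but its importance is minor. The branch needs a GFR below 45, a next-day value of 45 to 50, and a further value below 45. Few participants are likely to meet that sequence at week 6, though the documents give no figure from which to count them. Where KHCO3 is given, the capsule stop removes it. In Arm 2, where the stop removes nothing active, the named hazard is smaller.

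Three stronger readings are not supported. The text does not direct that whey continue; it fails to say. Nothing shows harm or bias: the 118 to 124 days are the time over which exposure could differ for someone who reached the branch, not an estimate of harm, and 118 is not a ceiling. Nor is any effect on the primary analysis implied, since ITT membership does not change. That mITT and per-protocol membership is unaffected rests on full prior adherence and on averaging compliance over both assigned products.

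**What to change.** In the third route, write: *the participant will stop study powder packets and capsules*. Name both products in that route's remain-on and continue-taking sentences and in the ITT retention sentence. If a capsule-only stop was intended, state why.

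The SAP (3a) describes the trial as already conducted. If treatment has ended, report in the safety results what was done with the powder for anyone who reached this branch, or that no one did.

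The cost is a few words in one bullet, or one line in the report. The small downside of the amended rule is lost powder exposure in the few participants it would reach; they would stay in the ITT analysis.
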